Subject Exclusion Criteria	 Advanced comorbid conditions with life expectancy <1 year Patient is <18 of years of age Patient has a CRT device Female patients who is pregnant or not on a reliable form of birth control. Women of childbearing potential are required to have negative pregnancy test within the 7 days prior to device implant Unwilling or unable to return for required follow-up visits Patient decides study participation is cost-prohibited
Duration of Exposure	At the 12-month follow-up, when each subject completes his/her cross- over 6-month therapy, the CRT (Edora HF-T QP, or Ilivia HF-T QP DF4) function will be programmed on to provide chronic benefit from CRT for a battery life of 8.6 years.
Reference therapy	Patients are self-referenced as a cross-over design.
Statistical Methodology	 The primary endpoint is the change in LVESVI. We will compare the changes in LVESVI between CRT-ON and CRT-OFF groups. We will explore 5-10 metabolomic factors as principal components to predict group differences (using a 2-sample t-test), and response to CRT therapy. In particular, we will relate these principal components to response to CRT using multiple linear regression (for the LVESVI endpoint) and Cox Regression (for the Clinical endpoint).

RESEARCH STRATEGY

A. Background and Significance

Heart failure is a progressive disease with high mortality and morbidity. Heart failure (HF) affects 5.7 million American adults and claims nearly 300,000 lives annually.¹ HF progresses along a continuum from asymptomatic (Stage A and B) to symptomatic (Stage C and D).² Nearly three times as many people with left ventricular (LV) systolic dysfunction are in Stage B as in Stages C and D combined.^{3,4} In the Framingham Heart Study, total mortality rates within four years of symptomatic HF development were 24% in women and 55% in men.⁵ In the community, the prevalence was 6% for those with a left ventricular ejection fraction (LVEF) of 50% or less and 2% for those with an LVEF of 40% or less.⁶ This translates to 4% of the population who have mild LV systolic dysfunction with LVEF between 41%-50%.⁷ Although the risk of hospitalization or death declines as LVEF increases, an LVEF in the range of 36% to 50% still confers a considerable risk of adverse outcomes. For instance, the CHARM study showed that patients with an LVEF between 33%-52% had annual cardiovascular mortality rates in the range of 4.0%-6.0% and HF hospitalization rates of 5.7%-7.2%.⁸

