We propose a single-center, randomized cross-over study design. The study will be approved by the Mayo Clinic Institutional Review Board, and a consent form will be signed by each participant. We will enroll 100 patients at Mayo Clinic, Rochester, Minnesota, who have LVEF of 35% to 50%. Of these patients, 30 will be women. Participants will undergo placement of a CRT-pacemaker (CRT-P) after the completion of the baseline assessment if all inclusion and none of the exclusion criteria are met. Participants who have an ICD in place, or who meet clinical indication for an ICD, will undergo placement of a CRT-defibrillator (CRT-D). Defibrillation will not be added for patients who do not have an existing ICD system or do not meet clinical indications for an ICD. Participants who have a successful CRT implantation will be randomly assigned 1:1 to have the CRT programmed on (CRT-ON, treatment group) or off (CRT-OFF, control group) within 7 days of completing the implant procedure. Participants will be randomly assigned using an allocation method defined by a biostatistician. Investigators managing HF in study participants will be blinded to the randomization method to minimize potential bias. A washout period after the device implantation will not be used in this study.¹⁹ At 6-month follow-up, the CRT function will be turned on in the CRT-OFF group and the CRT function will be turned off in the CRT-ON group in a cross-over design. All participants will cross-over at the 6-month follow-up visit. At 12-month follow-up, when each patient completes his/her cross-over 6-month therapy, the CRT function will be programmed on to provide chronic benefit from CRT for a battery life of 8.6 years. The subjects will be blinded from whether biventricular pacing is on or off. For participants who receive a CRT-D, the defibrillation function will be programmed on for the duration of the study.

Study device

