Primary safety objectives

Freedom from system-related complications in randomized participants will be calculated at 1, 6, and 12 months post-implant to determine the safety profile, including the device pocket hematoma, pneumothorax, myocardial perforation, lead dislodgment, lead revision, and device-related infection. This safety profile will be balanced against efficacy to quantify the risk-benefit ratio. This analysis will occur when all subjects have completed study procedures.

Sample Size Considerations and Statistical analysis

The timing of primary endpoint analysis will occur when all subjects have completed study procedures. The primary endpoint for Aim 1 is the change in LVESVI. We propose a paired t-test, which combines both

randomized groups together (n=50 + 50 = 100), and compares the CRT-ON condition to the CRT-OFF condition. The power can be estimated based on REVERSE (LVEF \leq 40%) showing a mean change of -18.4 +/- 29.5 ml/m2. Let us assume that in the current mildly impaired EF group, the reduction will be, not -18, but -12. Assuming the SD is 26, the power for the one-sample paired t-test is over 99%. If we assume an 80% attrition (n=40 + 40), the detectable difference with 80% power is 8.3 ml/m2, less than half of that observed in REVERSE. A secondary analysis will be a generalized linear model in which baseline, period 1, and period 2 values of LVESVI will be analyzed together, with the possibility of an order effect. If no order effect is detected, then the analysis will amount to the paired t-test already described. Data may be missing due to the occurrence of interim events. This would mean that the data are not missing at random. We propose to accommodate this by a rank-based procedure, in which the ON-OFF differences are ranked in both groups together. As a secondary endpoint, we will analyze the composite clinical endpoint described above. This endpoint will be analyzed as the time to the first of any of these component events. The crossover design can be accommodated by fitting the treatment variable ON-OFF as a time dependent binary variable that is 1 (ON) or 0 (OFF). Order effects can be accommodated by including interactions with time-period in the model.

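### The primary LVESVI paired t-test pools both randomised sequences without a period term; a period-adjusted crossover analysis would protect it at almost no cost

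*Combined protocol and SAP*

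**What the plan says.** Under Study design and randomization, patients are allocated 1:1 to start with CRT on or off, and all switch at 6 months. Under Sample Size Considerations and Statistical analysis:

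- The primary test is a paired t-test that takes the two "randomized groups together (n=50 + 50 = 100), and compares the CRT-ON condition to the CRT-OFF condition". No period or sequence term is named.
- The power statement is: "Assuming the SD is 26, the power for the one-sample paired t-test is over 99" per cent, for an assumed reduction of 12 ml/m2. With 40 + 40 patients the detectable difference at 80% power is given as 8.3 ml/m2.
- A secondary generalized linear model follows, in which the baseline and both period "values of LVESVI will be analyzed together, with the possibility of an order effect". The plan adds: "If no order effect is detected, then the analysis will amount to the paired t-test already described". It does not say whether the term means a period effect or carry-over, and it does not describe the case where an effect is detected.
- On missing data: "Data may be missing due to the occurrence of interim events", which the plan takes to mean that data are not missing at random. Its answer is a rank-based procedure "in which the ON-OFF differences are ranked in both groups together".

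For the composite clinical endpoint only, the same section says that order effects can be handled through interactions with time-period.

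**The concern.** In a two-period crossover, anything that shifts LVESVI between month 6 and month 12 in both sequences (disease progression, for example) enters the ON-OFF difference with opposite signs in the two sequences. A pooled paired t-test relies on equal numbers to cancel that shift from the mean, and it leaves the shift in the error term. Two things are at stake: some lost power even when completion is equal, and bias in either direction when it is not. The plan itself expects interim events to cause missing data, so unequal completion is possible. The secondary model, which could adjust for period, is described as reducing to the same unadjusted test when no order effect is detected.

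**Working it through.** **Inputs.** From the plan: effect 12, SD of ON-OFF differences 26, n = 100 or 80 (40 + 40, read as 80 completers). Assumed: two-sided alpha 0.05, period effects *p* of 6 or 12 ml/m2, and the completer splits. The documents give none of these.

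**Plan's own figures.** Noncentral t, noncentrality δ√n/SD. For n=100: 12 × 10/26 = 4.62, power 99.5%. For n=80 the detectable difference at 80% power is 8.24, against the stated 8.3. Both reproduce.

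**Model.** Let *p* be the common shift in LVESVI from period 1 to period 2. The mean ON-OFF difference is −12 − *p* in ON-first patients and −12 + *p* in OFF-first patients.

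- Pooled mean: −12 + *p*(n_OFF-first − n_ON-first)/N. The last term is the bias.
- SD seen by the pooled test with equal numbers: √(26² + *p*²).

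**Equal completion, 40 + 40, *p* = 12.** Bias is zero. The apparent SD is √(676 + 144) = 28.6, so the estimated SE is 28.6/√80 = 3.20, while the mean still varies with SE 26/√80 = 2.91.

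- Type I error: the threshold is about 1.99 × 3.20 = 6.37, and 6.37/2.91 = 2.19, giving about 2.8%. Simulation gives 3.0-3.1%.
- Power at 8.3: entering SD 28.6 in the noncentral t gives 72.6%. Using the actual SE of the mean, (8.3 − 6.37)/2.91 = 0.66, or about 75%; simulation gives 74.5%. With no period effect it is 80.5%.
- For *p* = 6: apparent SD 26.7, type I error 4.4%, power at 8.3 about 78%.
- At the plan's effect of 12 and *p* = 12, power is still 98.6% (n=100) and 95.9% (n=80).

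**Unequal completion, N = 80, true effect zero.**

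| Completers | *p* | Bias (ml/m2) | Type I error, pooled (simulated) |
|---|---|---|---|
| 45 vs 35 | 12 | 12 × 10/80 = 1.5 | 5.4% |
| 48 vs 32 | 6 | 6 × 16/80 = 1.2 | about 6% |
| 48 vs 32 | 12 | 12 × 16/80 = 2.4 | 9.2-9.6% |

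The period-adjusted test stays near 5% in every row. If 80 of 100 patients complete independently of sequence (hypergeometric), 79% of trials fall within 42 vs 38, 2.3% reach 45 vs 35 or worse, and fewer than 1 in 10,000 reach 48 vs 32.

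**Period-adjusted analysis.** The estimate is the simple average of the two sequence means, with SE = (26/2)√(1/n1 + 1/n2) on N − 2 df.

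- 50 + 50: SE 2.60, the same as 26/√100; power 99.5%.
- 40 + 40: SE 2.91; detectable difference 8.25; power 80.5% at 8.3 for any *p*.
- 48 + 32: SE 13 × 0.228 = 2.97, a small price for removing the bias.

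**Carry-over.** If benefit L remains at the OFF echocardiogram of ON-first patients, the expected effect is 12 − L/2. For L = 6 it is 9. Power (n=100/80) is then 92.6%/86.0% for the pooled test and 92.9%/86.4% for the period-adjusted test, so the period term does not help here.

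**Six-month comparison.** Two-sample test on unadjusted change, assuming SD 26: SE = 26√(2/50) = 5.2, power 63%, 95% CI half-width 10.3. At 40 per arm, power is 53% and half-width 11.6. The crossover half-width at n=100 is 5.2.

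**The case against.** The strongest reply is that the defect is nearly harmless. Allocation is 1:1, equal completion gives no bias, and at the plan's effect of 12 power hardly moves. Medical therapy is to be kept stable, which limits one source of drift. Nothing in the documents says that dropout will depend on sequence, and chance alone will almost never produce 48 vs 32. A period-capable secondary model is already planned, and the composite-endpoint text suggests that the authors had period terms in mind. All of this stands and keeps the point modest. It does not remove it, because the secondary model adjusts for period only if the order effect means a period effect and the term is kept.

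The rank-based procedure might also keep patients with interim events in the analysis and so reduce imbalance. The text does not say how missing values are ranked or which test follows, so this can be neither credited nor excluded.

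Stronger readings a reader might infer, which the documents do not support:

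- *A preliminary order test chooses the primary analysis.* The paired t-test is primary unconditionally. The quoted sentence says only what the secondary model reduces to.
- *The overview contradicts the analysis section.* The Statistical Methodology row says "We will compare the changes in LVESVI between CRT-ON and CRT-OFF groups", which could suggest a parallel-group comparison. The Reference therapy row of the same table makes each patient his or her own reference, and the analysis section specifies the paired test.
- *Carry-over could create a false positive.* Persisting benefit pulls the estimate towards zero. The later OFF echocardiogram also follows about 6 months OFF, which acts as an implicit washout, although the documents do not say whether that is long enough.

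**Conclusion.** The point holds as a modest improvement to the primary analysis. Under equal completion the cost of omitting period is a conservative test and some lost power: about 6 to 8 percentage points at a difference of 8.3 with 80 completers and a period effect as large as the treatment effect. Under unequal completion the cost is bias of *p*(n1 − n2)/N, reaching 2.4 ml/m2 and a type I error of about 9% in the most adverse case examined. Those sizes rest on assumed period effects and completer splits and on two-sided 0.05. The adverse case requires dropout related to sequence, which the plan's own missing-data statement makes possible but does not predict. Carry-over is a separate limitation that the period term does not cure.

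**What to change.** 1. Make the primary analysis the treatment-plus-period (sequence-adjusted) crossover comparison of ON vs OFF. Keep the period term whatever an order test shows, and replace the sentence on no order effect being detected with that rule. Say whether order effect means period or carry-over for LVESVI.
2. Stratify the rank-based procedure by sequence in the same way, for example by ranking period 1 minus period 2 differences and comparing the two sequences.
3. State that the period term does not remove carry-over, and that persisting benefit would make the estimate conservative. As a supportive sensitivity analysis only, report the baseline-adjusted ON vs OFF comparison at 6 months. The 63%/53% power above is for unadjusted change and may differ with baseline covariance adjustment. It is too imprecise to replace the crossover estimate.

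The cost is analysis-plan wording, one degree of freedom and one extra model on echocardiograms already scheduled at screening, 6 and 12 months. Power stays 99.5% at n=100, and the detectable difference stays at about 8.3 ml/m2 with 40 + 40. No sample-size change is needed.

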Effective treatment of HF in the early stage by CRT. This study proposes to investigate the novel use of CRT in patients who have mild HF, with a decreased LVEF of 35% to 50% and a LBBB. This patient population is at high risk for progression from mild to severe HF, which represents an increasing burden to the community and the health care system. Reversal of myocardial dysfunction in the early stage, before it becomes irreversible, is a sound and innovative strategy.

C. Approach

Preliminary results

Mild HF and clinical outcomes

We screened the Mayo Clinic electrocardiography (ECG) database for patients with a diagnosis of LBBB from 1994 through 2014. Among 12,879 patients identified, 1,436 patients met the criteria of having transthoracic echocardiography (TTE) within one-year of the ECG diagnosis of LBBB and a LVEF of 36% to 50% (**Figure 1**). These study patients were matched 1:1 to 1,436 patients without LBBB on the basis of age, sex, baseline LVEF, and year of TTE. The mean (SD) age in both groups was 67 (13) years, and 54% were men. Clinical outcomes were compared between the LBBB and control groups.

Long-term survival. The Kaplan-Meier 20-year probability of survival in both groups is shown in **Figure 2**. Patients with mild HF (LVEF 36%-50%) and LBBB had lower survival rates at 5 (72% vs. 76%; P=.04), 10 (53% vs 61%; P<.001), and 20 years (27% vs 46%; P<.001) compared with the controls who had a normal QRS duration.

LVEF deterioration to <35%. The event-free rates of the LVEF reduction to <35% at 1 year (83% vs 89%) and 5 years (63% vs 70%) (hazard ratio, 1.34; 95% CI, 1.09-1.63; *P*=.005—were lower in the LBBB group than the control group. This finding suggests that, compared with a normal QRS duration, the presence of LBBB in patients with mild HF led to a greater LVEF deterioration with time, which could be attributed to ventricular dyssynchrony.

Implantable cardioverter-defibrillator and CRTdefibrillator implantation. The survival free of an implantable cardioverter-defibrillator (ICD) or CRTdefibrillator (CRT-D) placement in the LBBB group was lower than the control group (87% vs 92% at 1 year; 80% vs 88% at 5 years) (hazard ratio, 1.73; 95% CI, 1.30-2.30; P<.001). Thus, patients in the LBBB group reactived ICD/CBT D more often than the

LBBB group received ICD/CRT-D more often than the non-LBBB control group. This finding is consistent with evidence of greater LVEF deterioration in the LBBB group.

1.0

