Device pacing settings will be programmed in the DDDR mode at 60 to 150 beats/minutes. The CRT-ON or CRT-OFF will be programmed according to the randomization. Patients will be called at 1-month to evaluate for potential pocket discomfort and procedure-related complications. Patients will return for follow-up at 6-month (initial program CRT-ON or CRT-OFF) and 12-month (cross over program CRT-ON or CRT-OFF). Peripheral blood will be drawn for metabolomic study, and echocardiography, 6-minute walk, KCCQ, and NYHA class will be assessed at each follow-up. Patients will undergo standard clinical care to maximize CRT response. Device function will be closely monitored on a daily basis via a remote monitoring system. Patients will continue a stable medical therapy through entire study to minimize confounding due to drug changes during the study. Any adjustment in medications, if clinically needed, will be carefully recorded and we will take into consideration the confounding drug effect in analysis. After patients complete the study, they will be followed annually by phone to assess adverse events.

Schedule of Events

	Screening (within 90 days of implant)	Device Implant (Day 0 ± 4 days)	Post- Implant (Day 0 ± 4 days)	1 Month Phone Call (± 7 days)	6 Month (±30 days)	7 month (± 7 days)	12 Month (± 30 days)	24, 36, & 48 Month Phone Calls (± 30 days)
Echocardiogram (may include 3D echo imaging)	X ²				x		х	
Physical exam	х				х		х	
12-Lead ECG	х		х					

Six-minute walk test	х				х		х	
Kansas City Cardiomyopathy Questionnaire (KCCQ)	х				х		х	
Chest X-ray			Х					
Pregnancy test (if applicable)	X ¹							
Blood collection For biomarker analysis	Х	x			х		х	
Device programming/ interrogation			x		Х		Х	
SAE/AE Assessment (heart failure symptoms, pocket pain, device function, etc.)			x	х	х	х	х	х
Medication Reconciliation	Х		х	х	Х	х	х	

1. Females of child-bearing potential must have a negative pregnancy test within 7 days of device implant.

2. Imaging can be done within 12 months of implant.

Metabolomic analyses

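### Is the handling of missing LVESVI pairs left so open that the primary result is in doubt?

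*Combined protocol and SAP*

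**What the plan says.** The relevant text is in the combined protocol and SAP, under Sample Size Considerations and Statistical analysis. It opens with "The primary endpoint for Aim 1 is the change in LVESVI" and continues at once with "We propose a paired t-test, which combines both" randomised sequences and compares ON with OFF. The power statements follow and rest on that test: over 99% with 100 patients, a difference of 12 and an SD of 26; and with 80 patients, "the detectable difference with 80% power is 8.3 ml/m2".

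A generalized linear model is then called secondary and is said to reduce to the same paired test if no order effect is found. Next comes missing data caused by interim events. The plan comments "This would mean that the data are not missing at random" and answers with "We propose to accommodate this by a rank-based procedure, in which the ON-OFF differences are ranked in both groups together".

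Under Device programming and follow-up: "Patients will return for follow-up at 6-month (initial program CRT-ON or CRT-OFF) and 12-month (cross over program CRT-ON or CRT-OFF"). Each patient therefore has one echocardiogram per setting, and missing either one leaves no ON-OFF difference.

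**The concern.** Three things are unstated: whether the rank procedure replaces or supports the t-test, what rank a patient without a pair receives, and which test uses the ranks.

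Each could matter. If only observed differences are ranked, the procedure is a complete-pairs analysis and leaves out the patients it was introduced for. If ON-OFF differences were ranked and then compared between the two sequences, the CRT effect would cancel and only a period effect would be tested. If two analyses of the primary endpoint exist and neither is named as deciding, the choice could be made after the data are seen.

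The situation is also likely to arise. Background and Significance cites "annual cardiovascular mortality rates in the range of 4.0%-6.0" per cent, and Preliminary results reports that patients with LBBB "had lower survival rates at 5 (72% vs. 76%; P=.04"). Some of 100 patients will probably lack a pair because of an event.

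**Working it through.** **Inputs.** From the plan: 100 patients, effect -12, SD of the paired difference 26, and 80 retained pairs with a detectable difference of 8.3. Assumed: two-sided 5% (the plan states no level), normal differences, and 4 to 6 patients without a pair.

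**1. The plan's own figures.**
- Power at n = 100: 12/(26/√100) = 4.62, and Φ(4.62 − 1.96) = 99.6%. The noncentral t gives 99.5%, which agrees with over 99%.
- Detectable difference at n = 80: (1.96 + 0.84) × 26/√80 = 8.14. The t version gives 8.24, and power at 8.3 is 80.5%.

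Both reproduce as a two-sided 5% paired t-test on complete pairs, so this is the test on which the trial is sized.

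**2. How many pairs might events remove?** Five-year survival of 72% is 1 − 0.72^(1/5) = 6.4% mortality a year. The cited cardiovascular mortality is 4 to 6% a year. The chance of at least one death among 100 patients in 12 months is 1 − 0.96^100 = 98.3% to 1 − 0.94^100 = 99.8%, or 86.7% at an assumed 2%. So 4 to 6 lost pairs is a reasonable illustration.

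**3. Complete pairs under non-random loss.** Patients with the largest volumes are lost at one cut-off common to both settings. Residual SD is 26/√2 = 18.4, and between-patient SD is assumed to be 0, 18 or 30. True effect is -12:

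| Without a pair | Mean difference, between-patient SD 0 / 18 / 30 |
|---|---|
| 4% | -10.85 / -11.36 / -11.59 |
| 5% | -10.76 / -11.21 / -11.51 |
| 6% | -10.53 / -11.14 / -11.45 |

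The bias is 12 − 11.59 = 0.4 to 12 − 10.53 = 1.5 ml/m2, toward no effect. Power is 98.3-99.2% for the t-test and 97.7-98.9% for the signed-rank test. With no effect, ON and OFF are exchangeable under a common cut-off, so the tests stay valid. Simulated false ON benefit is 2.1-3.0% (t) and 2.1-2.8% (signed-rank) against 2.5%. With 4,000 trials the simulation standard error is √(0.025 × 0.975/4000) = 0.25 points.

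**4. Does the choice of analysis change the conclusion?** Here an event under ON takes the rank most unfavourable to ON, an event under OFF takes the most favourable, and events fall at random between settings. The t-test uses complete pairs; the signed-rank test uses all patients. The table shows how often they disagree on significance:

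| Pairs + events | At -12 | At -8.3 |
|---|---|---|
| 100 + 0 | 0.3% | 3.6% |
| 99 + 1 | 0.5% | 5.2% |
| 96 + 4 | 1.1% | 9.3% |
| 95 + 5 | 1.5% | 11.0% |
| 94 + 6 | 2.1% | 12.4% |

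The first row is the baseline: two different tests disagree this often with nothing missing. Accepting whichever test is significant gives 6.8-7.1% two-sided error with 4 to 6 events, against 5.9% for the same two tests with no missing data.

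**5. Which rank test?** The t-test is described as combining both groups, and the rank sentence uses parallel wording. A signed-rank test on the pooled differences fits both. A between-sequence rank-sum test of ON-OFF differences would reject in about 5% of trials at -12, against 99% for the pooled signed-rank test. A statistician would not choose it to test CRT.

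**The case for a change.** The strongest opposing case is that the plan itself calls the loss non-random and offers the rank procedure as its answer, so a reader could take that procedure as decisive. The missing rule would then carry weight. With 80 pairs plus 5 events at -8.3, power is 80.3% for the t-test and 70.3% for the rank test, and they disagree in 14.7% of trials. If all 20 patients lost in the attrition scenario were events split evenly between settings, power at -12 would be 98% on complete pairs and 88% with extreme ranks. If every missing patient were ranked against ON, disagreement with 4 to 6 events would be 6-16% at -12 and 30-50% at -8.3. If loss of the largest 5% occurred only under ON, the complete-pairs mean would be -13.0 to -14.0, overstating the benefit.

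Part of this stands. The rank rule and the test are not written down anywhere, and ranking only the observed differences would not do what the procedure is for.

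The larger figures carry less weight. Ranking every missing patient against ON appears nowhere in the documents, and it would count a death under OFF against ON. Treating all 20 lost patients as events goes well beyond the 4 to 6 that the quoted mortality suggests. Loss confined to ON is a stress test, not an expectation. The value 8.3 is what 80 pairs can detect with 80% power; the effect the plan assumes is -12. At 8.3 any two reasonable tests will sometimes differ.

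Extreme ranks are not clearly better as the deciding analysis either. They mix events with volume and give no estimate in ml/m2. With 5 events all under OFF and no effect on volume, they favour ON in 11.5% of trials.

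**Conclusion.** The omission is real, but it is missing detail and not an error of method. Read naturally, the paired t-test decides: it follows the endpoint, carries both power figures, and is the test to which the secondary model reduces. The rank procedure supports it where events remove data, as a pooled signed-rank test. A trial statistician would fix the rank for patients without a pair, and the handling of ties, in the ordinary course of writing the analysis programs before unblinding.

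On that reading the conclusion is secure at the planned effect. The t-test has 98-99% power, bias is 0.4 to 1.5 ml/m2 toward no effect, false ON benefit is not inflated, and the two analyses disagree in 1-2% of trials. At -8.3 the disagreement is 9-12%, of which about 3.6 points come simply from using two tests.

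These figures assume 4 to 6 lost pairs, normal differences with SD 26 and two-sided 5%. The power and bias figures also assume loss at a cut-off common to both settings; the disagreement figures assume events that are independent of volume and ranked by the setting in force. A much larger loss, or one confined to a single setting, would make the rank rule matter more. The documents give no reason to expect either kind of event-related loss.
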